## **Adverse Events**

All Adverse Events regardless of seriousness or relationship to Investigational Product, including those from the first visit planned in the Clinical Trial Protocol/signature of the informed consent form, are to be recorded on the corresponding page(s) included in the Case Report Form. Whenever possible, symptoms should be grouped as a single syndrome or diagnosis. The Investigator should specify the date of onset, intensity, action taken with respect to Investigational Product, corrective treatment/therapy given, outcome and his/her opinion as to whether there is a reasonable possibility that the Adverse Event was caused by the Investigational Product.

## **Serious Adverse Events**

In the case of a Serious Adverse Event the Investigator must immediately:

- SEND (within 1 working day, by email) the signed and dated corresponding page(s) in the Case Report Form to the representative of the Monitoring Team whose name, address and email number appear on the Clinical Trial Protocol, or to a designated Safety email number provided by the Monitoring Team, as well as to the Central Database number;
- ATTACH a photocopy of all examinations carried out and the dates on which these examinations were performed. Care should be taken to ensure that the participant's identity is protected and the participant's identifiers in the Clinical Trial are properly documented on all copies of source documents provided to the Sponsor. For laboratory results, include the laboratory normal ranges;
- Follow-up of any Serious Adverse Event that is fatal or life threatening should be provided within one additional calendar week. The treatment code will be unblinded for reporting of Serious Adverse Events that are unexpected and reasonably associated with the use of the Investigational Product.

Serious Adverse Events Follow-up

- The Investigator should take all appropriate measures to ensure the safety of the participants, including referral to a specialist if indicated. Notably he/she should follow up the outcome of any adverse events (clinical signs, laboratory values or other, etc) until the return to normal or stabilization of the participant's condition;
- In the case of any serious adverse event, the patient must be followed up until clinical recovery is complete and laboratory results have returned to normal, or until progression has been stabilized. This implies that follow-up may continue after the patient has left the Clinical Trial and that additional investigations may be requested by the Monitoring Team;
- In case of any serious adverse event brought to the attention of the Investigator at any time after cessation of Investigational Product and considered by him/her to be caused by the Investigational Product with a reasonable possibility, this should be reported to the Monitoring Team.

## **10.2 Pregnancy**

No known adverse interactions with pregnant or nursing mothers.

## **10.3 Waiver**

Expected efficacy endpoints specified in this trial (primary and secondary efficacy criteria) will not be considered as AEs and will not be subject to expedited regulatory reporting. They will be reported on specific outcome event forms, which should be sent within one (1) working day, by Email, to the Central Database number.

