#### **4.15 Adverse Medical Device Reactions / Medical Device Interactions**

*None*

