#### **9.1.1.1 Primary Criterion**

Composite success rate. Safety - no issues or reported adverse conditions.

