## **10. PATIENT SAFETY**

### **10.1 Adverse Events Monitoring**

#### **Definitions:**

An adverse event is any untoward medical occurrence in a clinical investigation participant administered a medical device and which does not necessarily have to have a causal relationship with this treatment.

A Serious Adverse Event is any untoward medical occurrence at any dose that:

- Results in death or;
- Is life-threatening or;  
Note: The term "life-threatening" in the definition of "serious" refers to an event in which the patient was at risk of death at the time of the event; it does not refer to an event that hypothetically might have caused death if it were more severe.
- Requires inpatient hospitalization or prolongation of existing hospitalization or;
- Results in persistent or significant disability/incapacity or;
- Is a congenital anomaly/birth defect;
- Is a medically important event:  
Medical and scientific judgment should be exercised in deciding whether expedited reporting is appropriate in other situations, such as important medical events that may not be immediately life-threatening or result in death or hospitalization but may jeopardize the patient or may require intervention to prevent one of the other outcomes listed in the definition above. These should also usually be considered serious.

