#### **13.7.1.1 Description of the Primary Variable(s)**

The primary efficacy endpoint is the composite cluster of the first occurrence, over the duration of study (randomization to study end date inclusive), of the following adjudicated events:

- Any skin conditions caused by the device to include irritations,
- Any allergic reactions,
- Any new medical conditions during the study.

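### Section 10.3 takes AE status and expedited reporting away from expected efficacy endpoints, while Section 13.7.1.1 makes harms the primary efficacy endpoint

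*Protocol*

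**What the plan says.** Protocol Section 10.3 (Waiver) covers "Expected efficacy endpoints specified in this trial (primary and secondary efficacy criteria". These "will not be considered as AEs and will not be subject to expedited regulatory reporting". Instead, "They will be reported on specific outcome event forms, which should be sent within one (1) working day" to the Central Database. Neither the Protocol nor the SAP says what makes an endpoint expected.

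Section 13.7.1.1 supplies the events: "The primary efficacy endpoint is the composite cluster of the first occurrence" of adjudicated events of three kinds. These are skin conditions caused by the device (irritation included), allergic reactions, and "Any new medical conditions during the study".

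Section 10.1 defines the AE broadly: "An adverse event is any untoward medical occurrence in a clinical investigation participant administered a medical device", whether or not the device caused it. It requires every AE to be recorded in the case report form. It defines the SAE in its own sentence, as an untoward medical occurrence that meets one of the listed seriousness criteria. Section 13.8.1.2 tabulates AEs by system organ class and preferred term, with a separate line for new pulmonary conditions.

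Two other places use the same split. The Safety Review part of Appendix 5 treats outcome events as separate from AEs. Section 11.1 says an outcome event is not to be a reason for stopping the device, and then names an adverse event as a justification for stopping it. The SAP does not address the question.

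**The concern.** A waiver of this kind makes sense where the endpoint is a disease outcome that is expected in the population and would flood the AE system. Here the listed primary-endpoint events are possible harms of the device. A site that follows 10.3 literally would put an allergic reaction on an outcome form and not on the AE page. A site that follows 10.1 would do the opposite. The AE tables in 13.8.1 could then understate device harms, or differ between sites for the same kind of event. A reaction that health authorities would normally hear about quickly would be exempt from expedited reporting. Nothing in either document says that an endpoint event meeting the AE or SAE definition still follows 10.1.

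**Working it through.** No sample size, power or alpha enters this point, so the check sets the texts side by side.

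**Step 1: do the endpoint events meet the AE definition?** The inputs are the three components in 13.7.1.1 and the definition in 10.1. A device-caused skin condition, an allergic reaction and a new medical condition are each untoward medical occurrences in a participant treated with a device. That is 3 of 3. None has an upper limit on severity, so some could also be serious, for example an allergic reaction needing admission to hospital.

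**Step 2: what does 10.3 change for such an event?**

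| Element | Where the usual rule stands | Effect of 10.3 as written |
|---|---|---|
| AE status, and so AE tabulation | 10.1, 13.8.1 | Expressly removed |
| Expedited regulatory reporting | 10.1 (seriousness criteria refer to it) | Expressly removed |
| Form to the Central Database | 10.1: SAE pages in 1 working day | Outcome form in 1 working day; difference 1 − 1 = 0 |
| Copy to the Monitoring Team or safety address | 10.1, SAEs | Not mentioned |
| Examination copies; one-week follow-up of fatal or life-threatening events | 10.1, SAEs | Not mentioned |
| Pharmacovigilance database entry | Appendix 5, SAEs | Not mentioned |

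Two elements are waived in terms. The last three rows depend on whether the event still counts as an SAE, and 10.3 does not speak to that.

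**Step 3: does another section override the waiver?** The recording rule in 10.1 and the tables in 13.8.1.2 cover all AEs, but 10.3 says these events are not AEs. The sections conflict and no order of precedence is given. The reference in 10.1 to unexpected SAEs concerns breaking the treatment code, not the scope of 10.3. Appendix 5 repeats the separation.

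**Step 4: what still captures the event?** It is adjudicated (Appendix 4) and reviewed by the data monitoring committee (Appendix 5). The crude percentage with a primary endpoint is reported (13.7.1.2.3), and the cause of every death is validated (Appendix 4). These steps do not fully replace AE handling. Data for the committee's safety review are supplied quarterly, against 21 days of participation (6.2). The Day 7, 14 and 21 looks in 6.3 have no stated content or reviewer. The crude percentage has no stated breakdown by component or severity, so a mild irritation and a severe allergic reaction could count alike.

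**The case against.** The best defence is that 10.3 was meant for something narrower. Its parenthesis speaks of efficacy criteria, which is the heading of 9.1.1, where the content is mainly spirometry and oximetry. Section 4.15, "Adverse Medical Device Reactions / Medical Device Interactions", lists none, so a skin or allergic reaction is hard to call expected. This reading is possible, but three features of the text weaken it:

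- Section 10.3 deals in outcome events sent on event forms within a working day. Scheduled SpO2 and spirometry readings would hardly need a waiver from AE status.
- Section 13.7.1.1 is the only place that lists primary-endpoint events.
- The primary criterion in 9.1.1.1 itself reads "Composite success rate. Safety - no issues or reported adverse conditions", so moving to Section 9 does not take harms out of the criteria.

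A second objection is that this only follows from the plan's unsettled primary endpoint: SpO2 in 5.1, spirometry and oximetry in 9.1.1, the appearance of cystic fibrosis in 13.7, and the harm composite in 13.7.1.1. That is fair in part. If the endpoint were settled on SpO2 or spirometry, 10.3 would lose most of its reach over harms. But 13.7.1.1 is the explicit description of the primary variable, and the correction to 10.3 works however that question is resolved.

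A third objection is that the safeguards make the matter small. They do limit it, because the event reaches the database on the same deadline and the monitoring committee sees it. They do not restore AE tabulation or expedited reporting.

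**Conclusion.** The conflict holds and should be fixed. As written, the plan withdraws AE status (with tabulation under 13.8.1) and expedited regulatory reporting from events that are AEs by its own definition. This assumes that 13.7.1.1 is the operative primary endpoint and that its events count as expected, a term the plan leaves undefined. The number of events affected cannot be estimated, because the scope of the waiver is ambiguous and 10.1 and 13.8.1.2 still call for AE recording and tabulation. This is a safety-reporting fault. Section 10.3 by itself changes no estimate or test.

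Two stronger readings are tempting and are not supported:

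- A reader might infer that a serious harm loses all SAE handling, including examination copies, one-week follow-up and pharmacovigilance entry. Section 10.3 does not mention SAEs, and 10.1 defines them directly from the untoward occurrence, without requiring AE status first. Loss of these steps is a possible consequence if a site reasons that what is not an AE cannot be an SAE.
- A reader might infer from 11.1 that a participant with an allergic reaction must stay on the device. The guidance does conflict, and it discourages withdrawal, but it leaves the decision to the investigator's judgment and lets the participant stop at any time.

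**What to change.** 1. Delete 10.3, or limit it to the SpO2 and spirometry measurements.
2. Add one sentence: any event that meets the AE or SAE definition is recorded and reported under 10.1 and tabulated under 13.8.1, whether or not it is also an endpoint.
3. State in 11.1 that such an event may justify stopping the device.
4. Amend the sentence in the Safety Review part of Appendix 5 that separates outcome events from AEs, so that an event can be both.

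The cost is a wording change in three places (10.3, with the added sentence, 11.1 and Appendix 5), slightly more AE and SAE paperwork, and a safety profile that may look less favourable. The composite in 13.7.1.1 can stay or go. That decision belongs with settling the primary endpoint and need not delay this correction.

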## **11. HANDLING OF PATIENT WITHDRAWAL**

### **11.1 List of Withdrawal Criteria**

Occurrence of an outcome event according to the judgment of the Investigator must not be considered as a reason for study medical device discontinuation.

Depending on the Investigator's judgment, permanent study medical device discontinuation is only clearly justified for an adverse event, when qualifying condition is not present, or when a patient demands to withdraw from study medical device treatment, and in such cases the appropriate follow-up until the study end date should still be continued.

Although participants may withdraw from the study medical device at any time and for any reason, (or may be withdrawn at the Investigator's decision), patient withdrawal should be avoided as much as possible. If this occurs, every attempt should be made to restart study medical device if medically appropriate, whatever the duration of discontinuation. The reason for study medical device discontinuation will be recorded on the CRF. In any case, appropriate follow-up for efficacy and safety endpoints should be continued.

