### **8.10 Treatment Compliance**

Compliance is assessed by counting the number of returned bottles if any at each visit. The Investigator (or delegate) must complete the appropriate pages of the treatment log form and of the CRF. A discontinuation is defined as a period with a least three consecutive days without study medical device intake.

The study shall be open enrollment but patients must have access to the clinical location for clinical survey reporting. The survey must be completed two (2) times per week during the 21 day long trial. Potential participants should reside in the United States.

The monitor supervising the study will verify the data by comparing the recorded data with the investigational product retrieved.

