#### **13.6.1.2 Measurement of Treatment Compliance**

Treatment compliance for each patient will be calculated as the number of days study medical device was actually used (ie, number of days on treatment minus days of temporary discontinuation) divided by the number of days of follow-up, allowing for early permanent discontinuation of study medical device when applicable. Study medical device discontinuation is defined as a minimum of 3 consecutive days without study medical device intake. The percentage of participants at least 80% compliant will also be reported.

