## **26. CLINICAL TRIAL PROTOCOL AMENDMENTS**

All appendices attached hereto and referred to herein are made part of this Clinical Trial Protocol.

The Investigator should not implement any deviation from, or changes of the Clinical Trial Protocol without agreement by the sponsor and prior review and documented approval/ favorable opinion from the IRB/EC of an amendment, except where necessary to eliminate an immediate hazard(s) to clinical trial participants, or when the change(s) involves only logistical

or administrative aspects of the trial. Any change agreed upon will be recorded in writing, the written amendment will be signed by the Investigator and by the Sponsor and the signed amendment will be filed with this Clinical Trial Protocol.

Any amendment to the Clinical Trial Protocol requires written approval/favorable opinion by the IRB/EC prior to its implementation, unless there are overriding safety reasons.

In some instances, an amendment may require a change to the Informed Consent Form. The Investigator must receive an IRB/EC approval/favorable opinion concerning the revised Informed Consent Form prior to implementation of the change.

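### Section 11.1 says an outcome event must not be a reason to stop the device, but the only outcome events listed are skin, allergic and new medical conditions, and the rest of 11.1 allows the stop

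*Protocol*

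**What the plan says.** Three paragraphs of Protocol Section 11.1 govern stopping the device.

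- Paragraph 1: "Occurrence of an outcome event according to the judgment of the Investigator must not be considered as a reason for study medical device discontinuation". No exception is stated.
- Paragraph 2, subject to the Investigator's judgment: "permanent study medical device discontinuation is only clearly justified for an adverse event", and also when the qualifying condition is absent or the patient asks to stop.
- Paragraph 3: "participants may withdraw from the study medical device at any time and for any reason, (or may be withdrawn at the Investigator's decision", although withdrawal is to be avoided as far as possible.

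Section 13.7.1.1 defines the primary efficacy endpoint as the first of three kinds of adjudicated event. The first is "Any skin conditions caused by the device to include irritations"; the others are allergic reactions and new medical conditions. The secondary cluster in Section 13.7.2.1 shows no events after its colon in the text available, which may be a loss in extraction. The SAP does not address stopping the device and lists no outcome events.

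Two further clauses bear on safety. Section 26 allows departures from the protocol "except where necessary to eliminate an immediate hazard(s) to clinical trial participants". The follow-up rules for serious adverse events in Section 10.1 say: "The Investigator should take all appropriate measures to ensure the safety of the participants, including referral to a specialist if indicated".

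**The concern.** A rule against stopping treatment because an endpoint has occurred is ordinary when the endpoint is a measure of benefit or disease. Here the listed endpoint events are skin, allergic and new medical conditions, and the first is by definition caused by the device. The rule then reaches the events for which a clinician would most naturally rest or withdraw the device.

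Two sites could treat the same device rash in opposite ways and both cite 11.1: one continues under the first sentence, the other stops under the next two paragraphs. Section 13.3.2 calls for a summary of deviations in device administration, but the text does not settle which site deviated.

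A related uncertainty is whether these events count as adverse events at all. If they do not, the close monitoring that Section 11.2 requires after a stop for an adverse event, and the Section 13.8.1.4 summary of adverse events leading to discontinuation, would not clearly apply to them.

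**Working it through.** No arithmetic applies. The point depends on no alpha, power, event rate or sample size, and the plan states no figure to reproduce. The check is to set the sections side by side.

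1. **What is an outcome event?** Appendix 4 says that reported outcome events are defined in the protocol. Section 10.3 puts efficacy endpoints on outcome event forms. Appendix 5 sends primary outcome events to the Clinical Events Committee, and Section 13.7.1.1 describes its cluster as adjudicated events. That cluster is the only list of events in the documents, so it is the natural referent of the term in 11.1.

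2. **Does the first sentence of 11.1 reach device harm?** It states no exception, and the list includes device-caused skin conditions and any allergic reaction. Read literally, yes.

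3. **Does the rest of 11.1 resolve this?** Paragraph 3 permits the stop, by the participant or by the Investigator. Nothing says whether that permission or the opening prohibition prevails.

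4. **Does the adverse-event route in paragraph 2 resolve it?** Not securely.
   - For: Section 10.1 defines an adverse event broadly enough to cover a rash or allergic reaction. Section 13.8.1.2 counts new pulmonary conditions, which overlap the third listed event, among the adverse-event summaries.
   - Against: Section 10.3 removes expected efficacy endpoints from adverse events, Section 13.7.1.1 calls its cluster the primary efficacy endpoint, and Appendix 5 keeps outcome events apart from adverse events.
   - The scope of 10.3 is itself unclear. It refers to the efficacy criteria, and the Section 9.1.1 headings that match this term name no skin or allergic event; 9.1.1.1 mentions safety only in general terms.

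5. **Do the hazard and safety clauses resolve it?** They largely protect a participant with a serious reaction. Neither says whether a mild or moderate reaction is a permitted reason to stop.

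6. **Is the primary analysis affected?** Little. Sections 11.1 and 11.2 continue follow-up after a stop, and Section 13.7.1.2.3 counts events that occur after permanent discontinuation.

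**The case against.** The strongest reply is that this follows from another fault. Section 5.1 gives the primary outcome as change in SpO2, Sections 9.1.1 and 9.1.2 add spirometry, and Section 13.7 speaks of a reduced appearance of cystic fibrosis. If the outcome is a measurement, the first sentence of 11.1 is unremarkable. This stands in part: replacing the 13.7.1.1 cluster with SpO2 would end the conflict. As written, however, 13.7.1.1 and 13.7.1.2.3 are the operative primary-analysis text, and they are event-based.

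A second reply is that 11.1 can be read to mean that outcome status alone is no reason to stop, while an adverse event is. That reading is workable but not secure, because Section 10.3 and Appendix 5 cast doubt on whether these events are adverse events. It is also fair to say that sites could differ over a mild rash even without the first sentence, since paragraph 2 leaves the decision to judgment. What the first sentence adds is a prohibition against one of the two decisions.

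Three stronger inferences are not supported.

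- A reader might infer that a participant with a device reaction must stay on treatment. Paragraphs 2 and 3 allow stopping.
- A reader might infer that these events certainly drop out of adverse-event reporting. The text is unclear on this. In any case, 11.1 still puts the reason for stopping on the CRF, and 13.8.1.2 still counts permanent withdrawals.
- A reader might infer that shorter rests escape the prohibition, because Section 8.10 says "A discontinuation is defined as a period with a least three consecutive days without study medical device intake" and Section 13.6.1.2 says "Study medical device discontinuation is defined as a minimum of 3 consecutive days without study medical device intake". Those are definitions for measuring compliance; nothing states that they govern 11.1.

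**Conclusion.** The contradiction is real. The first sentence of 11.1 bars stopping for the listed events, and paragraphs 2 and 3 permit it. It rests on taking Section 13.7.1.1 as the list of outcome events, which the cross-references support and no other list displaces.

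It is a conflicting safety instruction, not evidence that anyone would be kept on the device against medical judgment. Serious reactions are largely covered by the Investigator's discretion, the immediate-hazard exception and the general safety duty, so the remaining exposure is mainly mild or moderate reactions. It concerns about 70 participants (Section 7.1), each active for 21 days (Section 6.2). With no reaction or discontinuation rates in the documents, the number of affected decisions cannot be estimated. It should be corrected, because the change is nearly free and bears on participant safety.

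**What to change.** 1. **Section 11.1.** Limit the first sentence to efficacy outcomes that are not harms, or delete it. Add that the device may be interrupted or permanently stopped for any skin, allergic or new medical condition when the Investigator judges this necessary.

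2. **Section 10.3 and Appendix 5, Safety Review.** State in 10.3 that the events listed in 13.7.1.1 are also recorded as adverse events, so that the monitoring in 11.2 and the summary in 13.8.1.4 apply. Amend the Appendix 5 sentence that separates outcome events from adverse events; otherwise it would contradict the new text.

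The cost is one sentence narrowed or deleted and one added in 11.1, one added in 10.3, and one amended in Appendix 5. No visits or participants are added. The small downside is that the same event is recorded on both the outcome event form and the adverse-event page and appears in both sets of tables, which a footnote can explain.

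If 13.7.1.1 is instead replaced by the SpO2 outcome of Section 5.1, the conflict disappears and both edits become clarifications only.
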